7.2. Missing Values

In general, missing values will not be replaced by imputed values.

- Patients who, for any reason, do not supply bone marrow for response assessment are counted among those not achieving remission
- Patients missing a time-to-event endpoint will have their value censored according to the rules set forth below (see sections 7.8.2 to 7.8.5)

Exceptions to the general rule of not replacing missing values are planned for the following items.

- The first day of the month will be used for a missing day component of a partial birthdate, and January will be substituted for a missing birth month (these substitutions are relevant only for calculating a patient's age)
- Partial start and end dates for adverse events will be replaced by calendar dates that maximize the duration of the adverse event (see section 7.10.2)

7.3. Visit Windows

Visit windows are not relevant for analyzing efficacy endpoints since these endpoints are either binary outcomes over the entire study period (e.g., CR rate) or measured on a continuous time scale (e.g., OS and PFS). Some safety assessments are summarized over time and within-cycle visit windows will be used (e.g., clinical laboratory parameters; see section 7.10.4).

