During both Induction and Reinduction, if necessary, care must be taken to ensure the patient's lifetime daunorubicin equivalent does not exceed $460 \text{ mg}/\text{m}^2$ (see [Appendix G](#) for conversion table) or that their left ventricular ejection fraction (LVEF) does not drop below 45%.

No intra-patient escalation of the alvocidib dose is permitted.

Consolidation – HiDAC

Consolidation therapy with HiDAC may be initiated at the time of hematologic recovery or within 90 days of recovery. Consolidation therapy may start before complete hematologic recovery after discussion with the Medical Monitor. It is not anticipated that all patients will undergo Consolidation therapy.

The HiDAC regimen will consist of 3 gm/m² IV every 12 hours on Days 1, 3, and 5 (a reduced dosage of 1.5 gm/m² is permitted for patients aged 60 to 65 years) (ie, a total of 6 doses over the 3-day regimen). The starting dose of HiDAC may be decreased pending discussion between the investigator and Medical Monitor.

Patients who plan to receive chemotherapy-based consolidation should get a minimum of two cycles of Consolidation up to a maximum of four cycles. Patients proceeding to stem cell transplant for Consolidation should get one cycle of Consolidation, if possible, to ensure disease stability while transplant plans are being made.

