5.4.5 Consolidation – Response Assessment

- After Consolidation cycles 2 and 4, patients will undergo response assessments including MRD via peripheral blood and bone marrow biopsy samples collected at the time of hematologic recovery (ie, ANC >1000/ μ L and platelet count >100,000/ μ L). These same samples will also be used for assessment of other potential biomarkers. Central laboratory assessment of MRD is to be done for disease assessment and treatment guidance. If the bone marrow biopsy and/or aspirate is nonproductive or not diagnostic, the procedure must be repeated within 7-10 days.
- Additional bone marrow samples may be requested at the discretion of the Investigator.
- Assess for AEs
- Record only those medications (prescription, nonprescription, nutritional supplements) administered in conjunction with an AE.

5.4.6 Consolidation – Cycles 2 through 4

Patients who plan to receive chemotherapy-based consolidation should get a minimum of two cycles of Consolidation up to a maximum of four cycles. Patients proceeding to stem cell transplant for Consolidation should get one cycle of Consolidation, if possible, to ensure disease stability while transplant plans are being made.

Each cycle will include the assessments listed in Section 5.4.1 through Section 5.4.5.

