7.2 Efficacy Endpoints

Since the primary objective of this study is to determine safety and tolerability including of alvocidib when administered over a range of doses followed by cytarabine/daunorubicin (7+3) in adults with newly diagnosed and previously untreated AML, a formal efficacy analysis is not appropriate. However, any objective response to treatment will be determined using the remission definitions detailed in the 2017 European LeukemiaNet Recommendations in AML [10] after Induction (or Reinduction) (definitions provided in Section 11.3.2).

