11.3.2 Efficacy Analyses

Objective response to treatment will be determined using the remission definitions detailed in the 2017 European LeukemiaNet Recommendations in AML [10] after Induction/Reinduction (for those patients not achieving a CR after Cycle 1) (see [Appendix E](#)).

- CR_{MRD-} = CR without MRD
- CR = Complete Remission (including patients with morphologic CR who are MRD+ and cytogenetic and/or molecular marker positive)
- CR_i = CR with incomplete hematologic recovery
- MLFS = Morphologic leukemia-free state
- PR = Partial Remission
- SD = Stable Disease
- PD = Progressive Disease

The numbers of overall complete remissions (patients with a best objective response of CR_{MRD}, CR, CR_i or MLFS), and overall remissions (patients with a best objective response of CR_{MRD}, CR, CR_i, MLFS or PR) will be summarized by observed rates and estimated 95% CIs. If there are sufficient numbers of patients achieving remissions for an analysis to be informative, logistic regression will be used to model the probability of achieving a remission as a function of the total alvocidib daily dose level (bolus dose amount + infusion dose amount) and biomarker prediction endpoints (eg, MRD).

Kaplan-Meier time-to-event analyses will be conducted on overall survival, relapse-free survival and duration of remission. Mortality (all causes) at 30 and 60 days will also be calculated. Cox proportional hazards models will be fit to these time-to-event endpoints with the total alvocidib daily dose level (bolus dose amount + infusion dose amount) and biomarker prediction endpoints (eg, MRD) serving as independent variables in the model.

Additional exploratory analyses may be performed to assist the sponsor in planning future studies.

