Cycle 1: period of time from the first dose of study drug until the start of study drug in cycle 2 or the start of alternative AML therapy other than supportive measures such as blood product transfusions (hence a patient whose first response assessment in cycle 1 is a CRi is considered to have achieved CR if neutrophils and platelets recover prior to initiation of cycle 2 or alternative AML therapy)

Combined CR Rate: percentage of patients who achieve a combined CR following treatment with alvocidib

Combined Remission Rate: percentage of patients who achieve a combined remission following treatment with alvocidib

CR Rate: percentage of patients who achieve a CR following treatment with alvocidib (see section 7.8.1)

Dose-Limiting Toxicity: Refer to the study protocol for the specific conditions and events that qualify as a dose-limiting toxicity (DLT)

Intent-to-Treat Population: all patients enrolled in the study regardless of whether they actually received study drug and regardless of whether evidence is found indicating they failed to meet study inclusion/exclusion criteria or had other protocol violations (see section 7.1)

Minimal Residual Disease Negative: Absence of gene fusion transcripts using standardized techniques such as multiparametric flow cytometry or next generation sequencing

Neutrophil Recovery: Absolute neutrophil count ≥1x10⁹/L following the administration of study drug

Per-Protocol Population: The subset of safety patients who either (a) have at least one response assessment on study, or (b) die prior to their first scheduled response assessment; however, patients are excluded from the per-protocol population if they have an important protocol deviation, such as when evidence is found indicating they failed to meet any study inclusion/exclusion criterion (see section 7.1)

Platelet Recovery: Platelet count ≥100x10⁹/L following the administration of study drug

Prestudy: Occurrence prior to the first administration of study drug

Safety Population: The subset of intent-to-treat patients who received at least one dose or partial dose of study drug (see section 7.1)

Shift Table: two-way frequency table pairing baseline value with the most extreme post-baseline result

Study Drug: alvocidib, Ara-C (cytarabine) and mitoxantrone

Treatment Failure: failing to achieve a CR, CRi or PR following induction therapy (see section 7.8.2)

4. Introduction

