7.8.1. Remission Rates

The primary efficacy endpoint is CR rate as assessed by the investigator following treatment with alvocidib. Patients who, for any reason, do not supply bone marrow for response assessment are counted among those not achieving remission.

Summary statistics will include the number and percentage of patients rated as not achieving CR due to not providing a bone marrow biopsy/aspirate, proportion of patients who achieve a CR and exact 95% CI estimated without stratification. Between—treatment-arm statistics will include the Mantel-Haenszel odds ratio and 95% CI estimated with stratification.

A standard logistic regression (LR) model will be estimated relating the probability of achieving CR as a function of baseline MCL-1 dependence. Results will be presented graphically as follows. Patients will be divided into groups according to which range of values their baseline MCL-1 dependence falls:

$$(0\%-\leq d_1), (d_1-\leq d_2), (d_2-\leq d_3), \dots, (d_8-\leq d_9), (d_9-100\%)$$

where $d_1,...,d_9$ are deciles for baseline MCL-1 dependence regardless of treatment arm. Empirical CR rates will be calculated for patients within each range and plotted alongside CR probabilities estimated from the LR model.

Other remission rates (e.g., combined CR rate and combined remission rate) will be summarized similar to CR rate.

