7.8.4. Relapse-Free Survival Following CR

RFS time is defined only for patients who achieve a CR during the study and is measured from the date of CR (Day 1) until (a) relapse after CR, or (b) death from any cause, whichever occurs first.

An additional rule for defining RFS time is:

 A patient found to have relapsed after missing one or more scheduled response assessments will have his RFS time end on the scheduled date for the first missed response assessment following the last confirmation of CR

Patients enrolled subsequent to protocol amendment 6 were scheduled to be followed for 2 years following the end-of-study visit, whereas patients enrolled prior to protocol amendment 6 were followed for only 30 days following the end-of-study visit unless they reconsented to the amendment-6, 2-year follow-up period. The definition of RFS time and the following rules for censoring RFS time apply to all patients regardless of follow-up duration.

Rules for censoring RFS time are:

- A patient with RFS continuing as of the date he is lost to follow-up will have his RFS time censored on the date of his last response assessment
- A patient with RFS continuing as of the database lock will have his RFS time censored on the date of his last response assessment

Summary statistics will include the number and percentage of patients who achieve a CR, the number and percentage of censored RFS times, quartile RFS times, 95% CIs for the quartile RFS times, and KM "survival" percentages with 95% CIs at select milestone times (e.g., 6, 12 and 18 months).

Two endpoints analogous to relapse-free survival following CR will be analyzed using similar methods.

- Relapse-Free Survival Following Combined CR (defined only for patients who achieve a combined CR during the study): time from the earliest date of combined CR (Day 1) until (a) relapse after combined CR, or (b) death from any cause, whichever occurs first
- Relapse-Free Survival Following Combined Remission (defined only for patients who achieve combined remission during the study): time from the earliest date of combined remission (Day 1) until (a) relapse after combined remission, or (b) death from any cause, whichever occurs first

Response categories included in "combined CR" and "combined remission" are delineated in Section 3.

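### The SAP gives its primary efficacy endpoint, CR rate, no end date, so a CR first reached after HiDAC can be counted for alvocidib plus 7+3

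*SAP*

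**What the plan says.** **SAP.** Section 7.8.1 states: "The primary efficacy endpoint is CR rate as assessed by the investigator following treatment with alvocidib". Section 3 defines the rate as "percentage of patients who achieve a CR following treatment with alvocidib (see section 7.8.1"), and Table 1 in 4.1 is equivalent. None of these gives a closing date or stops counting at HiDAC, transplant or other AML therapy. Section 7.3 explains that visit windows do not matter for efficacy because the endpoints are either measured on a continuous time scale or are "binary outcomes over the entire study period (e.g., CR rate"). Section 7.8.4 uses the same open window: "RFS time is defined only for patients who achieve a CR during the study".

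**Protocol.** Section 7.2 determines response by the 2017 ELN "Recommendations in AML [10] after Induction (or Reinduction"). Section 11.3.2 likewise places it "after Induction/Reinduction (for those patients not achieving a CR after Cycle 1"). Section 4.1 schedules the assessment at hematologic recovery or Day 50 (Day 60 with Reinduction), whichever comes first.

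**Consolidation.** Protocol 4.1 adds: "Consolidation therapy may start before complete hematologic recovery after discussion with the Medical Monitor". Protocol 5.4.5 adds: "After Consolidation cycles 2 and 4, patients will undergo response assessments including MRD".

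**The concern.** The protocol ties response to the regimen under study. The SAP's window stays open through up to four cycles of a different regimen. A patient short of CR after Induction/Reinduction can receive HiDAC, be reassessed on schedule and meet CR for the first time then. Nothing in the CR-rate definition keeps that CR out of the numerator.

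CR rate is the SAP's primary efficacy endpoint and its main activity signal. The same CR variable is the outcome in the MCL-1 logistic regression (7.8.1, 7.9) and the ROC analysis (7.9), so a late CR would carry into the biomarker result. The planned CR tables (SAP Table 3) have no end-of-induction split, so a reader of those tables could not separate the two kinds of CR.

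**Working it through.** The documents state no CR rate, target or power, so there is no figure to reproduce. The check compares definitions and then scales the difference.

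**Step 1: can a first CR after HiDAC occur and be recorded?** Yes.
- Protocol 4.1 allows Consolidation to follow the assessment at recovery or Day 50. A patient assessed at Day 50 without count recovery is at best CRi under Appendix E.
- Protocol 6.2 considers removal for non-response only when there is no CR, CRi, MLFS or PR, so responders short of CR may stay on study.
- Marrow is scheduled after HiDAC cycles 2 and 4 (5.4.5). It is also possible at the investigator's discretion and at End of Study (5.5).

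**Step 2: how is each path classified?**

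| Path | SAP 7.3, whole study | SAP 3, Cycle 1 rule | Protocol, after Induction/Reinduction |
|---|---|---|---|
| CR after Induction | CR | CR | CR |
| CR first after Reinduction | CR | Dropped, if Cycle 1 is taken literally as the window | CR |
| CRi, counts recover only after HiDAC starts | CR | Not CR | Not CR |
| MLFS or PR, CR only after HiDAC | CR | Not addressed | Not CR |

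The three columns give different numerators from the same data.

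**Step 3: consistency within the SAP.** Section 7.8.2 defines PFS treatment failure as no combined remission (CR, CRi or PR) following induction. MLFS is not in that set. A patient with MLFS after induction and CR after HiDAC is therefore a PFS treatment failure and a CR-rate success.

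**Step 4: size.** Let c be the CRs up to the end of Induction/Reinduction, k the first CRs after that point, and N the number of patients.
- Rate with cut-off = c/N; whole-study rate = (c + k)/N; difference = k/N, never negative.
- One late CR: 1/22 = 4.5 points (N of the SAP Appendix 2 sample table); 1/13 = 7.7 points (its 30/60 column); 1/40 = 2.5 points (Protocol 11.2 maximum).
- HiDAC cycles 0/1/2/3/4 in the sample table: 13/4/2/2/1 of 22. At least one cycle: 22 − 13 = 9. At least two, enough to reach a scheduled Consolidation assessment: 2 + 2 + 1 = 5.
- Ceilings on k/N: 9/22 = 40.9 points for any HiDAC; 5/22 = 22.7 points for two or more cycles. These are bounds and not expectations, because most patients starting HiDAC at hematologic recovery would already be in CR.
- Assumed range k = 0 to 2 at N=22: 0 to 2/22 = 9.1 points.

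Illustration, assuming 50% with the cut-off and exact 95% CIs:

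| CRs | Rate | 95% CI |
|---|---|---|
| 11/22 (k = 0) | 50.0% | 28.2 to 71.8 |
| 12/22 (k = 1) | 54.5% | 32.2 to 75.6 |
| 13/22 (k = 2) | 59.1% | 36.4 to 79.3 |

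**The case against.** **The SAP may already have a cut-off.** The Cycle 1 definition converts a first CRi to CR only if counts recover before cycle 2 or alternative AML therapy. The SAP lists cytarabine as study drug, so a HiDAC dose would plausibly end Cycle 1. SAP 4 also leaves response criteria to the protocol. This stands in part: it supports a cut-off for CRi. But CR rate does not cite Cycle 1, and among the planned tables only a tumor lysis table uses it. The rule is silent on MLFS and PR, and taken literally as the window it would remove Reinduction CRs that the protocol counts.

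**The protocol is not uniform.** Section 11.3.2 summarizes best response and 11.3.3 uses remissions over the study, so a whole-study count has some protocol support. This stands. It shows that the cut-off needs stating, but does not supply one.

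**Little depends on the rate.** Antileukemic activity is a secondary protocol objective, Protocol 7.2 says a formal efficacy analysis is not appropriate, and escalation rests on DLTs. This stands and limits the weight of the point.

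**Stronger readings the documents do not support.**
- A reader might infer that the SAP expressly counts CRs after HiDAC. No sentence says so; it follows from the missing end date and the remark in 7.3, whose purpose is to explain why visit windows are not needed.
- A reader might infer that such CRs are produced by HiDAC. A CRi that becomes CR may simply be late count recovery from Induction.
- A reader might infer that cohorts reaching Consolidation more often would look better for that reason alone. HiDAC normally starts at hematologic recovery, so reaching it is largely a result of response.

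**Conclusion.** The point holds as a defect in the endpoint definition. Following the SAP as written can credit alvocidib plus 7+3 with a CR first reached after HiDAC. The effect on the CR rate can only be upward, by k/N. The size is unknown and probably small: 4.5 points per patient at N=22, 2.5 at N=40. The assumed range of 0 to 2 patients in 22 (0 to 9.1 points) does not come from the documents, and the sample-table counts come from a layout template, so they serve only to show scale. The like-for-like comparison is the CR category alone, because the protocol's overall complete remission composite also includes CRi and MLFS. No hypothesis test, threshold or dose decision depends on the rate; what is affected is the reported activity signal, the MCL-1 analyses and agreement with the PFS definition.

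**What to change.** In SAP 3, 4.1, 7.3 and 7.8.1:
- Define the CR, combined CR and combined remission rates as responses documented after Induction/Reinduction and before the first dose of HiDAC, transplant or other AML therapy.
- State that CRs after Reinduction count, and align the Cycle 1 text with this.
- Report best response at any time on study in a separate row.
- Report MRD-negative CR both at the end of Induction/Reinduction and at any time. The protocol deliberately measures MRD during Consolidation, so later conversions should stay visible.

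The cost is SAP wording, one or two extra table rows, and a CR rate that may be slightly lower. No assessment or treatment changes.

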7.4. Interim Analysis

No interim analyses are planned. However, ongoing review of clinical data was performed during patient accrual and follow-up as required for dose escalation/de-escalation decisions.

7.5. Patient Disposition

The numbers of patients enrolled (ITT population), dosed (safety population) and included in the per-protocol population will be summarized by frequency counts within and across alvocidib dose levels. Time on study will be summarized as a continuous variable (mean, standard deviation, median, minimum and maximum values). Reasons for discontinuation will be summarized as a categorical variable (number and percentage of patients in each category). Relevant data supporting these summaries will be listed by patient within alvocidib dose level.

7.6. Baseline Characteristics

Patient age in years on the date of the first dose of alvocidib will be calculated by dividing the number of days since birth (Day 1) by 365.25. If body surface area (BSA) expressed in m² is missing in the study database, then it will be calculated using the formula⁶

$$BSA = \sqrt{\frac{W \times H}{3600}}$$

where *W* is the patient's weight in kg and *H* is the patient's height in cm.

Summaries of baseline characteristics will include descriptive statistics appropriate for continuous, time-to-event and categorical variables within and across alvocidib dose levels (see section 7). Separate summaries will be produced for the ITT, safety and perprotocol patient populations.

Baseline characteristics include demographic data (e.g., age, sex, race, ethnicity, height, weight and BSA); AML history (e.g., clinical onset of AML [de novo AML, prior MDS or prior leukemogenic therapy], time since AML diagnosis, peripheral blood and bone marrow blast percentages, cytogenetic risk group, frontline AML therapy and response to frontline AML therapy [see section 6]); MCL-1 dependence; and other medical history (e.g., baseline ECOG performance status, hemoglobin, leukocyte and platelet counts, and blood chemistry parameters assessing liver and kidney function). Reported medical history terms will be mapped to Medical Dictionary for Regulatory Activities (MedDRA) preferred terminology and then summarized within and across alvocidib dose levels by incidence rates for each MedDRA primary system organ class (SOC) and preferred term (PT). Optionally, depending on the perceived relevance, prestudy medications will mapped to terminology in the World Health Organization (WHO) Drug Dictionary Enhanced (DDE) and then summarized within and across alvocidib dose levels by usage rates for each WHO DDE anatomical and therapeutic class (ATC) and preferred (i.e., standardized) drug name. Relevant data supporting these summaries will be listed by patient within alvocidib dose level.

7.7. Study Drug Exposure

Patients' total exposures to study drugs and average exposures per treatment cycle will be calculated and summarized within and across alvocidib dose levels by the mean, standard deviation, median, minimum and maximum values. Numbers of treatment cycles received will be summarized as a continuous variable (by the mean, standard

deviation, median, minimum and maximum values) and as a categorical variable (by the number and percentage of patients in each category). Reasons for noncompliance with protocol-specified dosing schedules will be summarized as a categorical variable. Relevant data supporting these summaries (including actual infusion durations and expected doses based on BSA calculated from a patient's latest reported height and weight) will be listed by patient within alvocidib dose level.

